10.4.6 Infections

Infection site, start date, stop date, culture site, result, and organism will be listed for all infections for all subjects.

10.5 Clinical Laboratory Evaluation

Clinical laboratory measurements include serum chemistry, urinalysis, and hematology. Results will be standardized to the international system of units (SI), where possible. All clinical laboratory evaluations were analyzed at study sites or at local laboratories where each subject resides. Laboratory results and the change from baseline will be summarized by visit for subjects in the PP1 sample. Results for chemistry and hematology labs will be listed in separate listings.

All laboratory tests will be listed, but if there are duplicate laboratory tests for one study period then the earliest observation will be used in the table summaries and graphic displays. They will be sorted by subject ID, laboratory parameter and time of assessment. Laboratory normal ranges will be included and out-of-range flags (H or L) will be used to denote values that are above (H) or below (L) the relevant reference range. Reference ranges will be obtained from The Harriet Lane Handbook¹.

Spaghetti plots for baseline and post-screening visits will be created for liver function tests including: AST, ALT, alkaline phosphatase, GGT, total bilirubin, and direct bilirubin.

Autoantibodies and quantitative immunoglobulins results and the change from baseline will be summarized using descriptive statistics by visit for subjects in the PP1 and PP2 samples as well as listed in separate listings.

Subject serology will be summarized by number and percentages for subjects in the PP1 and PP2 samples. CMV and EBV Reactivation will be summarized by descriptive statistics by visit for subjects in the PP1 and PP2 samples. Serology and CMV and EBV Reactivation variables will also be presented in separate listings.

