## 6.6 FOLLOW-UP ASSESSMENTS

[figure not shown]
Frequency of visits and the number of assessments performed will depend on whether the patient is undergoing high-, medium-, or low-intensity follow-up (see Figure 3 and Appendices 1–3).

All participants who successfully withdraw from immunosuppression must complete 12 weeks of high-intensity follow-up, 104 weeks of medium-intensity follow-up, and 104 weeks of low-intensity follow-up (see Appendices 1–3). The 12 weeks of high-intensity follow-up will begin immediately after the last dose of immunosuppressant medication is taken.

All participants who remain off immunosuppression after successful completion of low- intensity follow-up will undergo 208 weeks (4 years) of Extended Follow-up as described in Appendix 4.

Participants who experience any episode of rejection after successful complete of immunosuppression withdrawal will move into the medium-intensity follow-up schedule (see Appendix 2) for 52 weeks after their LFTs have improved (see section 5.5.2). They will then be discharged from the study.

Participants who fail immunosuppression withdrawal will move into the medium-intensity follow-up schedule (see Appendix 2) for 52 weeks and then will be discharged from the study.

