## Appendix 2. Schedule of Events: Medium-intensity Follow-up

Monthly visit	Medium-intensity Follow-up 											
	M1	M2	M3	M4	M5	M6	M7	M8	M9	M10	M11	M12
	M13	M14	M15	M16	M17	M18	M19	M20	M21	M22	M23	M24
General Assessments												
Physical examination						X						X
Vital signs						X						X
Telephone consultation	X	X	X	X	X		X	X	X	X	X	
Adverse events	X	X	X	X	X	X	X	X	X	X	X	X
Concomitant medications	X	X	X	X	X	X	X	X	X	X	X	X
Study Site and Local Laboratory Assessments												
Hematology						X						X
Comprehensive chemistry						X						X
Liver panel	X	X	X	X	X		X	X	X	X	X	
Autoantibodies						X						X
Quantitative IgG						X						X
Glomerular filtration rate (creatinine and height)	X 											X
Hemoglobin A 1C	X 											X
Central Laboratory Assessments												
Whole blood–quantitative PCR for CMV reactivation 	X 					X						X
Whole blood–quantitative PCR for EBV reactivation 	X 					X						X
Liver Biopsies												
Liver biopsies 												X
Tolerance Assessments												
Whole blood–flow cytometry panel staining						X						X
Frozen PBMC–T-cell assays						X						X

 Participants enter medium-intensity follow-up after completing 3 months of high-intensity follow-up or after failing immunosuppression withdrawal (see section 5.3). Participants who have successfully completed immunosuppression withdrawal will remain in medium-intensity follow up for 24 months. Participants who fail immunosuppression withdrawal will remain in medium-intensity follow-up for 12 months and then be discharged from the study.

 Will be performed *only* at visit M1 and not at visit M13.

 Do not collect if last sample was collected less than 6 weeks before visit M1.

 Additional biopsies will be performed if necessary to rule out rejection.

 Will be performed *only* at the end of the second year (i.e., month 24) of medium-intensity follow-up for those who have successfully withdrawn. Will *not* be done for those who experienced rejection and have completed 1 year of medium-intensity follow-up.

 If a rejection episode occurs, samples for all mechanistic assessments that are scheduled for monthly visits M12 and M24 (except for whole blood–flow cytometry panel staining) will be collected at this time.

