5. ANALYSIS POPULATIONS

Intent to treat (ITT) sample will be defined as all subjects who have signed informed consent and are enrolled. For the purpose of these analyses enrollment is defined as beginning the screening process for participation in the study.

Per protocol (PP) samples will be defined as all subjects in whom immunosuppression withdrawal is attempted.

- Per protocol 1 (PP1) sample will be defined as all subjects in whom immunosuppression withdrawal is attempted.
- Per protocol 2 (PP2) sample will be defined as all subjects without inclusion/exclusion criteria protocol deviations in whom immunosuppression withdrawal is attempted.

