10.4.5 Change in Renal Function, Blood Pressure, Cholesterol, and Glucose Control

Renal function is measured by creatinine and GFR. The GFR for each subject will be estimated by the Schwartz Formula:

$$\text{GFR (mL/min/1.73 m}^2\text{)} = \frac{k(\text{height})}{\text{creatinine}};$$

where $k = 0.33$ in premature infants, $k = 0.45$ in full term infants to 1 year old, $k = 0.55$ in children 1 year old up to 13 years old, $k = 0.65$ in adolescent males greater than 13 years old (k remains 0.55 for adolescent females greater than 13 years old); height is measured in cm; serum creatinine is measured in mg/dL.

Renal function, blood pressure, cholesterol, and glucose results and their respective changes from baseline will be summarized by visit for subjects in the PP1, PP2 and the ITT samples by clinical phenotype.

Spaghetti plots for post-screening visits will be created for renal function measurements, blood pressure, cholesterol, and glucose.

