10.6 Vital Signs, Physical Findings, and Other Observations Related to Safety

10.6.1 Vital Signs

Descriptive statistics of vital signs results and change from baseline of vital signs will be summarized for the PP1 and PP2 samples. Data listings will be provided for vital signs measurements. They will be sorted by subject, vital sign parameter and time of assessment. Data reported in English units will be converted to corresponding metric units (e.g., cm, kg, degrees C).

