Appendix 2. Schedule of Events: Medium-intensity Follow-up

Monthly visit	Medium-intensity Follow-up ¹¹											
	M1	M2	M3	M4	M5	M6	M7	M8	M9	M10	M11	M12
	M13	M14	M15	M16	M17	M18	M19	M20	M21	M22	M23	M24
General Assessments												
Physical examination						X						X
Vital signs						X						X
Telephone consultation	X	X	X	X	X		X	X	X	X	X	
Adverse events	X	X	X	X	X	X	X	X	X	X	X	X
Concomitant medications	X	X	X	X	X	X	X	X	X	X	X	X
Study Site and Local Laboratory Assessments												
Hematology						X						X
Comprehensive chemistry						X						X
Liver panel	X	X	X	X	X		X	X	X	X	X	
Autoantibodies						X						X
Quantitative IgG						X						X
Glomerular filtration rate (creatinine and height)	X ²											X
Hemoglobin A _{1C}	X ²											X
Central Laboratory Assessments												
Whole blood–quantitative PCR for CMV reactivation ¹²	X ¹³					X						X
Whole blood–quantitative PCR for EBV reactivation ²	X ³					X						X
Liver Biopsies												
Liver biopsies ^{14, 15}												X
Tolerance Assessments^{16,17}												
Whole blood–flow cytometry panel staining						X						X

¹¹ Subjects enter medium-intensity follow-up after completing 3 months of high-intensity follow-up or after failing immunosuppression withdrawal (see section 5.3). Subjects who have successfully completed immunosuppression withdrawal will remain in medium-intensity follow up for 24 months. Subjects who fail immunosuppression withdrawal will remain in medium-intensity follow-up for 12 months and then be discharged from the study.

¹² Will be performed *only* at visit M1 and not at visit M13.

¹³ Do not collect if last sample was collected less than 6 weeks before visit M1.

¹⁴ Additional biopsies will be performed if necessary to rule out rejection.

¹⁵ Will be performed *only* at the end of the second year (i.e., month 24) of medium-intensity follow-up for those who have successfully withdrawn. Will *not* be done for those who experienced rejection and have completed 1 year of medium-intensity follow-up.

¹⁶ If a rejection episode occurs, samples for all mechanistic assessments that are scheduled for monthly visits M12 and M24 (except for whole blood–flow cytometry panel staining) will be collected at this time.

¹⁷ Do not collect for subjects who have failed immunosuppression withdrawal.

	Medium-intensity Follow-up ¹¹											
Monthly visit	M1	M2	M3	M4	M5	M6	M7	M8	M9	M10	M11	M12
	M13	M14	M15	M16	M17	M18	M19	M20	M21	M22	M23	M24
Frozen PBMC–T-cell assays						X						X

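### SAP 10.5 pools children off drug with children who failed withdrawal under the same M1–M12 visit labels, so its by-visit laboratory means mix drug states and shift when the failures leave after M12

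*SAP*

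**What the plan says.** **Laboratory tables.** SAP 10.5: "Laboratory results and the change from baseline will be summarized by visit for subjects in the PP1 sample". SAP 5 defines the sample: "Per protocol 1 (PP1) sample will be defined as all subjects in whom immunosuppression withdrawal is attempted". Autoantibodies, IgG and CMV/EBV results are also summarised by visit, in PP1 and PP2. None of these tables is split by phenotype or drug status.

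**Who attends the M visits.** SAP Appendix 2: "Subjects enter medium-intensity follow-up after completing 3 months of high-intensity follow-up or after failing immunosuppression withdrawal". Children who completed withdrawal stay 24 months (M1–M24). Children who failed stay 12 months (M1–M12) and are then discharged.

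**Late rejection.** Protocol 6.6: "Participants who experience any episode of rejection after successful complete of immunosuppression withdrawal will move into the medium-intensity follow-up schedule". This lasts 52 weeks after liver tests improve. Protocol 5.5.3.4 has maintenance drug reinstated once the episode resolves. Neither document gives these visits a label of their own.

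**Tables that are split.** SAP 10.4.5 covers renal function, blood pressure, cholesterol and glucose; results and "changes from baseline will be summarized by visit for subjects in the PP1, PP2 and the ITT samples by clinical phenotype". Its spaghetti plots start after screening, whereas the liver-test plots in 10.5 include baseline.

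**Vital signs.** SAP 10.6.1: "Descriptive statistics of vital signs results and change from baseline of vital signs will be summarized for the PP1 and PP2 samples". There is no split, and the section does not itself say that the table is by visit.

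**Duplicates.** SAP 10.5 keeps the first of several results in one study period. SAP 9.1.3 keeps the one nearest the target day and sends the rest to listings.

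**The concern.** A by-visit table is readable only if a visit label means roughly the same thing for every child in the column. Here it does not. For a child who completed withdrawal, M1 follows about three months off drug. For a child who failed during the taper, M1 follows the failure, and that child never reached complete withdrawal.

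The trial's safety question is what happens to children as drug is removed and afterwards. The liver panel, autoantibodies, IgG and viral PCR bear directly on it, and these are the results tabulated without a split. A reader could take a pooled M12 mean as the state of children off drug, or read a step after M12 as a late effect of withdrawal when it only reflects who has left the column.

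**Working it through.** **1. The plan's own scenarios.** SAP 3.7 gives 9/20 and 4/20 successes with exact binomial 95% intervals. Clopper-Pearson limits with n = 20 are:
- 9/20 = 45%: 23.06% to 68.47% (stated: 23.1%, 68.5%)
- 4/20 = 20%: 5.73% to 43.66% (stated: 5.7%, 43.7%)

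Both reproduce, so these scenarios serve as illustrations of group size.

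**2. Composition of an M6 or M12 cell.** Assume that all 20 children reach an M phase. With s successes, the failed share is f = (20 − s)/20.
- s = 9: f = 11/20 = 0.55
- s = 4: f = 16/20 = 0.80

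These are upper values. A child who completes withdrawal but fails within the first year counts among the failures and may still have off-drug M values.

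**3. Shift after M12.** Write A for the mean in children off drug and B for the mean in children who failed, and hold both constant over time.
- Pooled mean at M12: (1 − f)A + fB
- Mean once the failures have left: A
- Shift: A − [(1 − f)A + fB] = f(A − B)

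The step is therefore 0.55(A − B) or 0.80(A − B), from composition alone. By the Appendix 2 schedule it would first show at M13 for the monthly liver panel, and at M18 for hematology, comprehensive chemistry, autoantibodies, IgG and PCR.

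**4. Does the 10.4.5 phenotype split equal drug status?** SAP 3.3 defines tolerant as off drug for at least one year, and SAP 9.2.1 keeps a child who rejects after that year among the successes. High-intensity follow-up takes the first 12 weeks off drug, so one year falls 52 − 12 = 40 weeks into the M phase, or 40/(52/12) = 9.2 months.
- Rejection after about M9: the child stays tolerant but is then followed on reinstated drug under Appendix 2.
- Failure within the first year off drug: the child is not tolerant, yet may contribute off-drug M values to that column.

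The split therefore separates most but not all of the two states. This matters for GFR and hemoglobin A1c, whose first scheduled values after screening are at M1.

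**5. Second pass through Appendix 2.** If a late rejector's repeat visits carry M labels and are pooled, two such children in the 9/20 scenario give (11 + 2)/(20 + 2) = 13/22 = 59% of records from failed or re-treated children. If the duplicate rules apply instead, the two rules in 9.1.3 and 10.5 can keep different values. The precedence statement in SAP 4 concerns only that section's own conventions, so it does not settle which rule governs.

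**The case against.** The strongest reply is that the declared safety endpoint is already protected. Renal function, blood pressure, cholesterol and glucose are split by phenotype in 10.4.5. Graft safety does not rest on pooled means: the SAP provides individual liver-test plots from baseline, dysfunction listings, Banff severity by phenotype, Kaplan-Meier time to rejection and subject profiles. Every numeric summary prints n, so a fall from 20 to 9 would be visible. The SAP estimates no effect of being off drug, and finer columns in 20 children will be small and defined by what happened after baseline. All of this stands. It limits the consequence, but the 10.5 tables still mix the two groups.

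Some stronger readings are tempting but not supported:
- A reader might infer that the renal and metabolic endpoint is diluted to 0.45 or 0.20 of the true change. Those fractions (9/20, 4/20) assume pooling that 10.4.5 does not do.
- A reader might infer a reversed sign, as in 0.45D − 0.55D = −0.10D, with D the change from being off drug. That needs resumed drug to move a value by exactly −D, and no figure in the documents supports it.
- A reader might take every failure to be on rescue drug. Protocol 5.3 also counts as failures tapers suspended beyond four weeks and liver tests that do not substantially improve without rejection, and does not fix those children's regimens.
- A reader might assume that numbering restarts at M1 after a late rejection. The documents reuse the schedule but do not say this.

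**Conclusion.** The concern holds for SAP 10.5. Its by-visit tables pool children off drug with children who failed withdrawal at M1–M12. Up to 55% or 80% of an M6 or M12 cell is failures in the SAP's own scenarios, with a composition shift after M12 of 0.55 to 0.80 of the between-group difference. These figures assume that all 20 children reach an M phase and that group means stay constant. The size in clinical units is unknown, because the documents give no between-group difference.

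For 10.4.5 the problem is residual: phenotype is a final outcome, not drug status at the time of measurement. For 10.6.1 it applies only where vital signs are shown by visit, which 9.1.3 implies but 10.6.1 does not say.

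It would go too far to say that the reporting describes neither state, since listings, profiles and individual plots remain. The weakness lies in descriptive safety tables. The primary endpoint, the rejection analyses and the sample size are untouched. It is worth correcting before the tables are programmed, but the trial's main result does not depend on it.

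**What to change.** - In SAP 10.5, and in 10.6.1 where vital signs are shown by visit, present summaries separately by drug status when the sample was taken: tapering, off drug, or failed/immunosuppression resumed. At minimum, split by phenotype as 10.4.5 does.
- Add the same drug-status flag to the 10.4.5 tables.
- Label visits after failure or late rejection separately from the first pass through Appendix 2.
- State one duplicate rule for both 9.1.3 and 10.5.
- Include the screening value in the 10.4.5 spaghetti plots, as 10.5 does for liver tests.

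The dates are already collected. SAP 8 lists taper doses with start and stop dates. SAP 9.2.2 needs the dates of completing withdrawal and restarting drug. The medication records in SAP 12.1 can supply resumption dates for children who failed during the taper, whom the SAP 8 listing may not cover after failure.

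The cost is SAP wording and programming, with no new data. The drawback is fewer children per column, so the columns should be read as description only.

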The 10 other children, however, did not respond readily to treatment, including 3 who had recurrent or persistent CMV infection, of which 1 also had hepatic artery thrombosis; 1 who progressed to chronic rejection and underwent retransplantation; and 5 who progressed to *de novo* autoimmune hepatitis. These five were treated with immunosuppression designed for autoimmune hepatitis. All responded, although one has had several relapses of autoimmune hepatitis attributed to noncompliance. In retrospect, when late acute cellular rejection was diagnosed, three of these five already had histologic features suggestive of *de novo* autoimmune hepatitis (plasma cell infiltrates with perivenular dropout or bridging collapse) and two of five had detectable autoantibodies.

Therefore, the King's College experience suggests that uncomplicated late acute rejection responds readily to treatment. However, concurrent processes such as CMV infection or hepatic artery thrombosis make reversal of dysfunction more difficult. Moreover, serologic and/or histologic features of autoimmunity necessitate a different treatment approach (see section 1.2.3.1).

Posttransplant *de novo* autoimmune hepatitis was first described in 1995. Currently, the diagnosis can be made when a transplant recipient without previous diagnosis of autoimmune disease develops serologic evidence of autoimmunity (high immunoglobulin G titers with positive titers of antinuclear (ANA), smooth muscle (ASMA), mitochondrial (AMA) or liver-kidney microsomal (ALKMA) antibodies in conjunction with an allograft biopsy that shows histopathologic features of chronic hepatitis (portal and periportal hepatitis with lymphocytes and plasma cells, bridging collapse, and perivenular cell necrosis). Although this does occur in adult recipients, it has been reported more often in pediatric recipients, with an estimated incidence of approximately 5% (2%–11%).

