#### **1.2.4.3 The Current Trial**

There are several features of our trial design that should minimize the likelihood of an unfavorable outcome (Table 4). First of all, unlike previous controlled withdrawal studies, we are excluding all recipients who underwent transplantation for liver diseases that might recur.

Second, we require thorough biochemical, serologic, and histologic assessments aimed to detect recipients with subclinical allograft dysfunction to exclude them from participation. Only the King’s College group performed prewithdrawal biopsies; those with mild, nonspecific abnormalities were allowed to withdraw. A significant number of their patients who could not be successfully withdrawn developed exacerbations of the abnormalities evident on their initial biopsies rather than acute rejection.

Third, our protocol incorporates serologic screening for markers of autoimmunity before enrollment and periodically during the withdrawal phase with an aim to identify those who may be evolving

toward *de novo* autoimmune hepatitis. Although *de novo* autoimmune hepatitis clearly occurs spontaneously, outside of controlled immunosuppression withdrawal, we are certainly concerned that this condition would be exacerbated by gradual withdrawal of immunosuppression.

Fourth, our study enrolls only pediatric recipients of parental living-donor grafts. Although there is doubt that HLA matching and donor-recipient relatedness result in a significant immunologic benefit, there is nevertheless a distinct thread of literature that suggests limited immunologic advantage to the parental living-donor setting. Some centers have reported that, while the incidence of acute rejection is comparable between living- and deceased-donor transplantation, that the acute rejection episodes that occur after living-donor transplantation are less severe and that living-donor liver transplantation is associated with substantially lower risk of chronic rejection than deceased-donor transplantation.

Fifth, only parental living-donor recipients who are 4 or more years post transplant (compared with 2 years in the Kyoto report) are eligible for our withdrawal trial. Our patients will likely start on lower relative immunosuppression doses since they are further out from transplantation and have undergone more “natural weaning” by continued growth.

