### 4.3 EXCLUSION CRITERIA

1. Indication for transplantation liver failure due to autoimmune disease, such as autoimmune hepatitis, primary sclerosing cholangitis, or primary biliary cirrhosis.
2. Hepatitis B infection as defined by the presence of HBsAg or active treatment for hepatitis B.
3. Hepatitis C infection as defined by the presence of antibody against hepatitis C.
4. Serologic evidence of autoimmunity defined as abnormal antinuclear, anti-smooth-muscle, antimitochondrial, or anti-liver-kidney microsomal antibody titers greater than or equal to 1:160.
5. Transplantation of a second organ before, simultaneously with, or after liver transplantation; or liver retransplantation.
6. Aspartate or alanine aminotransferase (AST or ALT) greater than 2 times the upper limit of normal.
7. Total bilirubin and direct bilirubin, and either alkaline phosphatase or gamma-glutamyl transferase (GGT) greater than 2 times the upper limit of normal.
8. Clinically significant change in hepatic function in the past 26 weeks.
9. GFR less than 40 mL/min/1.73 m^2.
10. Immunosuppression with
  - a. a 50% dose increase in a current agent within 26 weeks of screening, *or*
  - b. more than one agent within 52 weeks of screening.
11. Any systemic illness requiring or likely to require immunosuppressive drug use.

12. Human immunodeficiency virus (HIV) infection.
13. Pregnancy or breastfeeding.
14. Unwillingness or inability to comply with study requirements and procedures.

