4. GENERAL ANALYSIS AND REPORTING CONVENTIONS

The following analyses and reporting conventions will be used:

- Categorical variables will be summarized using counts (n) and percentages (%) and will be presented in the form n (%). Percentages will be rounded to 1 decimal place.
- In general, in frequency tables of variables with different categories (e.g., for discontinuation reason, race): if no subjects belong to a certain category, including Missing, across all treatment groups, then the printing of this category should be suppressed. Otherwise, if the number of subjects in a category for a treatment group is zero, then a zero should be displayed for the number, and the percentage should be left blank.
- Numeric variables will be summarized using n, mean, standard deviation (SD), median, min, max. The min/max will be reported at same level of significance as original data. The mean and median will be reported at 1 more significant digit than the precision of the data and SD will be reported at 2 more significant digits than the precision of the data. Descriptive statistics will be displayed in the order: n, mean, SD, median, min, max

- Following SAS default rules, the median will be reported as the average of the two middle numbers if the dataset contains even numbers.
- Test statistics including t and z test statistics will be reported to two decimal places.
- P -values will be reported to 3 decimal places if greater than 0.001. If less than 0.001 than report '<0.001'. A p -value can be reported as 1.000 only if it is exactly 1.000 without rounding. A p -value can be reported as 0.000 only if it is exactly 0.000 without rounding.
- All statistical calculations will be performed using the SAS System version 9.1 (or higher).
- Tables and listings will be generated as RTF files with Courier New font, size 8. Figures will be generated as CGM files. Separate stacked files will be created for the tables, listings, and figures and converted to PDF prior to delivery.
- The program name, creation date, and data extraction date will be included in the footer of all displays (For example, Program: *Program Name* Creation Date: HH:MM/DDMMMYYYY Data Extraction Date: DDMMMYYYY)
- In general, columns with character values will have the header and column values left aligned. Numeric columns will be centered around their decimal place with headers also centered.

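### SAP 10.5 lists autoantibody titers and summarises them by visit, but no planned table gives the number of participants who newly reach 1:160 after withdrawal starts

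*SAP*

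**What the plan says.** - **Planned summary.** SAP 10.5: "Autoantibodies and quantitative immunoglobulins results and the change from baseline will be summarized using descriptive statistics by visit", in PP1 and PP2. The sentence goes on to say that the results are "as well as listed in separate listings". Autoantibodies and IgG are handled identically.
- **Content of the summary.** SAP 4: "Numeric variables will be summarized using n, mean, standard deviation (SD), median, min, max".
- **Flags.** SAP 10.5: "out-of-range flags (H or L) will be used to denote values" outside the reference range, with ranges taken from a paediatric handbook. No flag is tied to 1:160.
- **Contrast in the same section.** "Subject serology will be summarized by number and percentages", so a count was specified for viral serology but not for autoantibodies.
- **Numeric cut-off.** Protocol 4.3, item 4, excludes patients with "abnormal antinuclear, anti-smooth-muscle, antimitochondrial, or anti-liver-kidney microsomal antibody titers greater than or equal to 1:160". It is the only numeric autoantibody threshold in the documents.
- **Purpose.** Protocol 1.2.4.3: "our protocol incorporates serologic screening for markers of autoimmunity before enrollment and periodically during the withdrawal phase". The stated aim is to find children who may be moving toward de novo autoimmune hepatitis.
- **Draws at rejection.** Protocol 5.5.3.1 requires autoantibodies when rejection is diagnosed, unless drawn in the previous 4 weeks.
- **Which draws reach the tables.** SAP 9.1.3 sends to listings only the values that are unscheduled, out of window, or in window but not nearest the target day. SAP 10.5 tabulates only the earliest of duplicate tests in a study period.

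**The concern.** The protocol worries that withdrawal could exacerbate de novo autoimmune hepatitis, and serial autoantibody testing is one of its design safeguards. The question this poses is per child: how many participants who entered without serologic autoimmunity acquired it? A by-visit mean and mean change describe the group average at one time, which is a different quantity.

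The numeric handling is also awkward. Titers are dilution steps, and a negative result has no natural number, so a mean depends on how negatives are coded and is dominated by the top dilutions.

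Finally, draws at rejection are among the most informative. In the King's College series cited in Protocol 1.2.4.1, two of the five children who progressed to de novo autoimmune hepatitis already had detectable autoantibodies when late rejection was diagnosed. Such draws may never enter a table.

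At stake is the reporting of a safety signal. If the count is left to whoever reads the listings, the threshold, time window and denominator will be chosen after the data are seen.

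**Working it through.** **1. Is a conversion count planned anywhere?** SAP 9.2 (efficacy variables), 10.3 and 10.4 (adverse events and other safety tables) and 10.5 (laboratory) contain no count of participants reaching a titer, no shift table and no time to conversion.

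**2. Can the count be recovered from the by-visit tables?** Constructed example with assumed titers: 20 children, all at 1:20 at baseline, four later visits, one value of 1:160 at each visit, titers coded as reciprocals.

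- Scenario A: the same child is at 1:160 at all four visits, so one child ever converts.
- Scenario B: a different child is at 1:160 at each visit, so four children ever convert.

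At every visit, in both scenarios:

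- mean = (19 × 20 + 160)/20 = 540/20 = 27.0
- SD = √[(19 × 7² + 133²)/19] = √(18,620/19) = 31.3
- median 20, minimum 20, maximum 160
- mean change = 140/20 = 7.0

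| | Children ever ≥1:160 | n | Mean | SD | Median | Min | Max | Mean change |
|---|---|---|---|---|---|---|---|---|
| A | 1 | 20 | 27.0 | 31.3 | 20 | 20 | 160 | 7.0 |
| B | 4 | 20 | 27.0 | 31.3 | 20 | 20 | 160 | 7.0 |

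The tables are identical. The maximum shows that somebody was at 1:160; it does not show how many children or which.

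**3. Is the mean change interpretable?** A rise from 1:20 to 1:40 adds 20 and a rise from 1:160 to 1:320 adds 160, yet each is one doubling step. A mean change of 7.0 does not correspond to any child's change in scenario A or B, where the changes are 0 or 140.

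**4. Which draws are tabulated?** An unscheduled draw at rejection is in listings only (SAP 9.1.3). If two tests fall in one study period, the earliest is used (SAP 10.5), so a later, higher titer drops out of the table. Some draws at rejection do get in: Protocol 6.1 and SAP 9.1.3 let a for-cause biopsy within 6 weeks of a protocol-biopsy visit carry that visit's tests, and where a draw was made in the previous 4 weeks the earlier one stands.

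**5. What would a count deliver?** The SAP's own method is the exact binomial interval: lower limit = 2.5% quantile of Beta(x, n − x + 1), upper limit = 97.5% quantile of Beta(x + 1, n − x). Checked against SAP 3.7 with n = 20: 9/20 gives 23.1% to 68.5% and 4/20 gives 5.7% to 43.7%, both as stated. Applied to converters, with all 20 children below the cut-off at baseline:

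| Converters | Exact 95% CI |
|---|---|
| 0/20 | 0 to 1 − 0.025^(1/20) = 16.8% |
| 1/20 | 0.1% to 24.9% |
| 2/20 | 1.2% to 31.7% |
| 3/20 | 3.2% to 37.9% |

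**The case against.** The other side has real points.

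- **The data are not lost.** Every result is listed, and SAP 6 adds subject profiles. With 20 children, a sustained rise can be found by reading. This stands: the gap is in the tables. But a listing fixes no threshold, window or denominator in advance.
- **The maximum is reported.** A reader might infer that a single high titer would be averaged away. The documents do not support that, because SAP 4 includes the maximum, which would expose the value at that visit. The limit is narrower, as step 2 of the working shows.
- **1:160 is an entry criterion.** A reader might infer that the protocol names it as an on-study sign of de novo autoimmune hepatitis. It does not. The description in Protocol 1.2.4.1 speaks of positive titers, and also needs high immunoglobulin G and biopsy features. Using 1:160 during follow-up is a reasonable borrowing, and must be labelled as one.
- **A reader might derive an expected number of converters** by applying the protocol's incidence of about 5% (2% to 11%) to 20 children. That is the incidence of the disease. The documents give no rate of conversion to 1:160, so the calculation has no basis.
- **Other routes exist.** Unexplained dysfunction leads to biopsy (Protocol 5.5.1), dysfunction episodes are listed with a final diagnosis (SAP 10.4.4), and adverse events are tabulated by preferred term (SAP 10.3). These would catch clinical disease. A purely serologic change becomes an adverse event only if the investigator judges it clinically significant (Protocol 8.3.1).
- **Titers could be treated as categorical**, giving counts under SAP 4. No categories are specified, change from baseline implies numeric handling, and counts at each visit are still not counts of children who ever converted.
- **Precision is low.** One of 20 has an interval reaching 24.9%. True, but the same sample size limits every proportion in this trial, and the SAP reports those with exact intervals.

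**Conclusion.** The point holds as a reporting gap in a safety summary. New conversion is listed but not tabulated, and the planned by-visit tables cannot supply the number of children concerned: one and four converters produced the same output. Means and mean changes of dilution titers add little that can be interpreted.

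The size is modest. The data are collected and listed, autoantibodies are not a named primary or secondary endpoint, and the primary endpoint and sample size are untouched. What the present tables cannot provide is a statement such as none of 20 converted, upper 95% limit 16.8%. No claim is made about how many conversions to expect.

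The conclusion assumes that titers are handled numerically under SAP 4, as the wording on change from baseline implies. The example titers are assumed and serve only to show that the tables do not determine the count.

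**What to change.** In SAP 10.5, for autoantibodies only:

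1. Replace the mean and mean-change summary with n (%) and exact 95% CI of PP1 and PP2 participants who were below 1:160 at baseline and had any titer of 1:160 or higher after the start of withdrawal, for each antibody and overall. Use all draws, including unscheduled ones and those at rejection, as a stated exception to the tabulation rules in SAP 9.1.3 and 10.5. The baseline condition matters mainly in PP1, which can include participants with eligibility deviations.
2. Add a shift table of baseline against highest post-baseline titer category, with the categories and the coding of negative results fixed in advance.
3. Keep the numeric by-visit summaries for IgG, and keep the listings.
4. State that 1:160 is taken from exclusion criterion 4 as a serologic signal and is not a diagnosis.

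Cost: one table respecified and one added; no new visits or samples. Two limits should be footnoted. Titers come from study-site or local laboratories (Protocol 6.3), so reported dilutions may differ. Follow-up is also unequal: participants who fail withdrawal are discharged after 52 weeks of medium-intensity follow-up, while successful ones stay for years (Protocol 6.6). The number of draws per participant should therefore be shown beside the count.
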